2. GENERAL CONSIDERATIONS

2.1 Conduct of Analysis

An interim analysis (IA) on safety and immunogenicity data will be conducted in two parts after the last subject completed Visit 6 (i.e. Day 236). The first part (IA Day 85) will be performed after safety data up to Day 85 have been cleaned and immunogenicity samples of Day 1 and 85 have been analyzed. The first part (IA Day 85) will cover safety data up to Visit 4 (Day 85) and ELISA immunogenicity data from Visit 1 (Day 1) and Visit 4 (Day 85). The second part (IA Day 236) will cover safety data up to Visit 6 (Day 236, i.e. six months after the last vaccination).

Data from selected dose groups in the Main Study and data from respective dose groups from the Run-in phase will be pooled for this and all further analyses.

A preliminary immunogenicity analysis was done prior to the IA D 85 as described above. This analysis was described in a separate analysis plan and covered descriptive immunogenicity analysis of selected time points of subjects from the run-in phase only.

A final data analysis will be conducted once the last subject has completed the study, i.e. Visit 7 (Month 12). As part of this analysis, Serum Bactericidal Assay (SBA) results will be analyzed. Those results will only be available for a subset of subjects, that was randomly chosen from the set of subjects from the main phase who have both a Day 1 and Day 85 immunogenicity blood sample.

It is indicated in Section 7, which Tables, Listings and Figures (TLFs) are provided for IA D85 and IA D236.

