2.4 Blinding and Randomization

Subjects will be allocated to treatment groups via the EDC system. Eligible subjects will be randomized stratified by study site 1:1:1:1 in the Run-in Phase and stratified by study site, age group and baseline *B.b. s.l.* serostatus 2:2:1 in the Main Study Phase according to a randomization list created by a statistician. The study will be an observer-blinded trial, which will be conducted in a blinded manner for the study investigators, the sponsor including laboratory personnel, and the subjects. Only designated study staff who randomize subjects into treatment groups and perform preparation and application of the vaccinations will be unblinded. These unblinded study staff members will not be involved with trial conduct otherwise. An overview of persons who will be unblinded is provided below:

Unblinded:

- Designated study site staff who randomize subjects to treatment groups and are concerned with IMP handling (i.e. perform preparation and application of the study vaccine, maintain drug dispensing log detailing the dates and quantities of IMP administered to each subject). These unblinded study staff members will not be involved with trial conduct otherwise.
- CRAs responsible for monitoring of IMP handling and related data for verifying drug accountability during the study and performing overall drug accountability.
- Statistical team at the CRO performing statistical analyses for generation of safety data tables for the DSMB.
- DSMB members.

Blinded:

- Study participants
- Investigators and other study staff involved in general study conduct and safety assessments.
- All other CRAs (responsible for monitoring study data apart from IMP handling/drug accountability).
- All other sponsor and CRO staff including laboratory personnel at the sponsor's labs for immunogenicity assessments.

General unblinding of sponsor staff and ADMB will be done for the IA Day 85 after confirmation that all subjects performed Visit 6 or, in case of missing V6 visits, after the close of the time window for Visit 6. Interim analyses results will be distributed to selected sponsor representatives.

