2.8 Protocol Deviations

Protocol deviations will be reviewed in the Blind Data Review Meeting (BDRM) prior to interim analysis of D85. Deviations will be classified as minor or major deviations, based on the potential influence on the immunogenicity analysis.

Major protocol violations that lead to exclusion of a subject from the PP Population (see Section 2.10.3) will include but are not limited to the following:

- Subjects who received less than three vaccinations
- Subjects who received wrong vaccinations

- Subjects with substantial time window violations on vaccination visits (Visits 2 and 3)
 - Visit 2 (Day 29): +/- 7 days
 - Visit 3 (Day 57): +/- 10 days
- Subjects who fulfil exclusion criteria 2, 8, 9 and 14
- Subjects with other deviations that may affect immune response

Protocol deviation classification will be made on a case by case decision.

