2.10.3 Per-Protocol (PP) Population

The Per-Protocol (PP) Population will exclude all subjects from the mITT that fulfilled at least one of the major protocol deviation criteria as defined in Section 2.8. The PP Population will be defined in the BDRM that is conducted before IA Day 85. A second DRM is planned prior to the final analysis to review protocol deviations after the interim analysis.

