2.14 Changes in the Conduct of the Study or Planned Analysis

Statistical analysis will be conducted as described in this SAP. Any deviations or changes will be described and justified in the CSR.

- It was stated in the protocol that an interim analysis on safety and immunogenicity data will be performed after all subjects have completed Visit 6 (i.e. Day 236, six months after the last vaccination) and that this interim analysis will cover safety and immunogenicity data up to Visit 4 as well as safety data up to Visit 6. This interim analysis will be conducted in 2 parts, a IA Day 85 covering all safety data up to Day 85 and immunogenicity data from Day 1 and Day 85. The second part will cover all safety data up to Day 236 (see Section 2.1). The first part of the Interim Analysis only starts after the last subject completed Visit 6 or the time window for Visit 6 has elapsed.

- The following adjustments concerning statistical analysis as compared to descriptions in the protocol are included in this SAP: The protocol planned to only compare the two dose groups selected for the main phase and the placebo group. However, it was decided to include all dose groups in the comparison. In particular, the pair-wise comparison between the two dose groups selected for the main phase and the placebo group, respectively, will be part of the comparisons that will be performed.
- It was stated in the protocol that all time points up to Day 85 will be included in interim immunogenicity analysis. However, only Day 1 and Day 85 will be analyzed in the IA Day 85. All time points will be analyzed in the Final Analysis.
- Due to optimization of the ELISA assay, the definition for seroconversion for ELISA results was adjusted as compared to the protocol, see Section 5.2.
- Functionality of antibodies will be measured by a Serum Bactericidal Assay (SBA). Analysis of SBA parameters will be described in a separate SAP and is not part of the interim analysis described here.

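### Sponsor staff are unblinded for the Day 85 interim analysis while the Day 86-236 safety data, already collected, need not yet be clean, coded or frozen

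*SAP*

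**What the plan says.** The interim analysis is split into two parts. For the first, Section 2.1 of the SAP states: "The first part (IA Day 85) will be performed after safety data up to Day 85 have been cleaned". It adds that the "immunogenicity samples of Day 1 and 85 have been analyzed". Section 2.14 fixes the earliest start: "The first part of the Interim Analysis only starts after the last subject completed Visit 6 or the time window for Visit 6 has elapsed". For the second part, Section 2.1 says: "The second part (IA Day 236) will cover safety data up to Visit 6".

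On blinding, Section 2.4 provides: "General unblinding of sponsor staff and ADMB will be done for the IA Day 85 after confirmation that all subjects performed Visit 6", or after the Visit 6 window has closed where that visit is missing. It continues: "Interim analyses results will be distributed to selected sponsor representatives". The same section lists as blinded the investigators, the site staff who assess safety, and sponsor and CRO staff outside the few named unblinded roles. The unblinding sentence lifts the blind for the sponsor part of that list and for the ADMB, an abbreviation not explained in the text at hand.

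Two data review meetings are described. Section 2.8 places the first before the Day 85 analysis: "Protocol deviations will be reviewed in the Blind Data Review Meeting (BDRM) prior to interim analysis of D85". Section 2.10.3 places the other later: "A second DRM is planned prior to the final analysis to review protocol deviations after the interim analysis".

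**The concern.** Waiting for Visit 6 before unblinding protects how the visits are conducted. It does not protect what happens to the data afterwards. Sending a query, choosing a MedDRA term and reviewing a possible adverse event of special interest all involve judgement, and that judgement is protected from bias only while the person exercising it does not know the treatment.

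SAEs, AESIs and unsolicited AEs are secondary safety endpoints (Section 1.3.2). The Day 236 interim analysis is their read-out six months after the last vaccination, with Fisher-type tests between groups (Section 6.1.3). If part of the data behind it is still being processed after sponsor staff know the allocation, its classifications could be questioned, although every Visit 6 contact was finished before the blind was lifted.

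**Working it through.** The SAP gives no figure on this point, so the check is of the order of events, followed by a count of what is exposed.

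**Order of events**

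1. *Collection.* All Visit 6 contacts are done, or the window has closed, before the first interim part starts (Sections 2.1, 2.4, 2.14). Follow-up to Day 236 is therefore over.
2. *Cleaning.* The only safety data that must be clean for the first part are those up to Day 85 (Section 2.1). No cleaning condition covers Day 86-236.
3. *Unblinding.* Sponsor staff are generally unblinded for the first part. The stated trigger is Visit 6 completion or window closure (Section 2.4). No cleaning, coding or freezing condition is attached.
4. *Reporting.* The second part then reports safety data up to Day 236 (Section 2.1).
5. *Coding.* AE-log terms are coded with the MedDRA version current at the interim data snapshots (Section 6.1.2.3). Section 2.13 refers to a Coding Guideline. Neither says who codes, whether they remain blinded, or whether the Day 236 snapshot comes before or after unblinding.

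Between steps 3 and 4, the Day 86-236 data may thus be open while sponsor staff know the treatment. Section 2.14 explains that the protocol foresaw one interim analysis and that the SAP splits it, but it does not address this interval.

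**How much is exposed**

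- Days: 236 - 85 = 151; 151/236 = 0.64. This is a share of nominal follow-up time, not of events.
- Tables in Section 7.1.4 marked both for the Day 236 analysis and for a statistical test: 14.1.4.1 to 14.1.4.13 (13) and 14.1.4.48 to 14.1.4.59 (12), so 13 + 12 = 25.
- Two of these are essentially closed to events after Day 85. Table 14.1.4.5 is by vaccination period, and the third period ends 28 days after the third vaccination, nominally 57 + 28 = Day 85 (Section 6.1.2.3). Table 14.1.4.10 concerns withdrawal from further vaccination, and for AE-log events this means that the second or third dose was not given.
- Remaining: 25 - 2 = 23. These tables are cumulative, so they also contain Day 1-85 events, which had to be clean before the first part.

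**Which judgements are involved**

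- Assignment as solicited or unsolicited hardly matters here. Diaries cover seven days after each vaccination (Section 1.5.2, note 22), and the last vaccination is at Day 57.
- Missing seriousness, severity or causality has a worst-case rule (Section 2.7), which limits discretion, although a query could still fill the field.
- Causality and seriousness are analysed as reported in the eCRF (Sections 6.1.2.1 and 6.1.2.3), and investigators are not named for unblinding.
- What remains is the choice of queries, MedDRA coding and medical review of AESIs.

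**The case against.** The strongest reply is that the harm is inferred from silence. A reader might conclude that unblinded staff will clean and code the Day 86-236 data. The SAP does not say so: it does not state that sponsor staff query, code or review adverse events at all. If blinded CRO staff do this work, the exposure is small. Section 2.3 also lists SOPs on interim analysis, on randomization and unblinding, and on data review meetings. These, like the Coding Guideline, are not shown and may already contain the safeguard.

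A reader might also infer that the lack of a blind review meeting before the Day 236 analysis removes a protection. The text does not support this. The blind meeting classifies protocol deviations by their possible influence on immunogenicity, settles the Per-Protocol Population and allocates subjects with vaccination errors (Sections 2.8, 2.10.1, 2.10.3). It is not given AE coding or AESI review, and the Day 236 analysis contains no immunogenicity (Section 5).

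Nor does Section 2.4 contradict itself by unblinding sponsor staff generally while sending results to selected representatives. Who may know the allocation and who receives results are separate matters.

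All of this stands, and it narrows the point. It does not remove it: the SAP states an unblinding rule for sponsor staff in general, and nothing in the document keeps those who handle adverse events outside it.

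**Conclusion.** The point holds as a gap in the unblinding rule. As written, sponsor staff in querying, coding or medical review roles may work on Day 86-236 safety data with treatment known, before those data are tested between groups at the Day 236 interim analysis. The exposed period is 151 of 236 days, and about 23 tested AE tables can take in its events. How many events fall in that period, and how large any bias would be, cannot be computed from the document.

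The conclusion assumes that some sponsor staff hold such roles and that no unseen procedure already keeps them blinded. If either assumption fails, only a clarification is needed. The stronger inference, that the trial's main result is compromised, is not supported: the primary analysis is of Day 85 GMTs and is unaffected. This is an inexpensive improvement to an interim safety read-out.

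**What to change.** In Section 2.4, replace the general unblinding of sponsor staff with a limited one, for example: *For IA Day 85, only the statistical team performing the interim analysis and the selected sponsor representatives who receive its results will be unblinded. All staff who query, code or medically review adverse events remain blinded until the safety data up to Day 236 have been frozen.* State separately whether, and why, the ADMB is unblinded at this point. In Section 2.1, name the Day 236 safety snapshot and its place in the sequence. If an existing SOP already ensures this separation, a cross-reference to it is enough.

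The cost is SAP wording and a documented firewall among existing staff, with no new data or subjects. The alternative is to clean, code and freeze the safety data up to Day 236 before any general unblinding. That needs no firewall, but it delays the Day 85 results and gives up much of the benefit of the two-part split, so it suits only a sponsor willing to accept the delay.

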1.2 Study Design

This is a randomized, observer-blind (subject, sponsor and investigator/ site staff involved in clinical evaluation of subjects are blinded), placebo controlled, multicenter Phase 2 study (see Figure 1).

In the Run-in phase, a total of 120 subjects aged 18 to 40 years were to be randomized stratified by study site 1:1:1:1 to receive VLA15 90 µg w/ alum, VLA15 135 µg w/ alum, VLA15 180 µg w/ alum, or placebo (30 subjects per treatment group) as intramuscular (I.M.) vaccinations on Days 1, 29 and 57. Dosing was to be adjusted by injection volume (see Table 1).

Table 1: Treatment Groups and Vaccinations

Group	Treatment	Injection Volume [mL]	Days of Vaccination
90 µg	VLA15 90 µg w/ alum	0.50	1, 29, 57
135 µg	VLA15 135 µg w/ alum	0.75	1, 29, 57
180 µg	VLA15 180 µg w/ alum	1.00	1, 29, 57
Placebo	PBS	1.00	1, 29, 57

Two safety visits were to be performed after the first vaccination: a safety phone call at Day 4 (i.e. Visit 1a, three days after the first vaccination) and an in-person visit at Day 8 (i.e. Visit 1b, seven days after the first vaccination). After all subjects enrolled in the Run-in phase completed Visit 4 (Day 85, i.e. 28 days after the third vaccination) a Data Safety Monitoring Board (DSMB) reviewed all available safety data up to Day 85 in a scheduled DSMB meeting and gave the recommendation that all treatment groups were safe and well tolerated so far and could be continued in the Main Study phase based on available safety data. After the DSMB meeting, the two higher dose groups (135 µg and 180 µg of VLA15 w/ alum) were selected for further investigation. No safety concerns associated with any of the VLA15 treatment groups were identified by the independent DSMB.

In the Main Study phase, a total of 450 subjects aged 18 to 65 years will be randomized stratified by study site, age group and baseline *B.b. s.l.* serostatus 2:2:1 to receive 135 µg or 180 µg VLA15 w/ alum (180 subjects each) or placebo (90 subjects), as I.M. vaccinations on Days 1, 29 and 57. Subjects will be enrolled in two age groups (18-49 years and 50-65 years) in a ratio of approximately 2:1.

In both study phases, target is to enroll approximately 10 % or more of subjects that are baseline seropositive for *Borrelia burgdorferi sensu latu* (*Bb s.l.*). This is aimed to be achieved through selection of endemic recruitment areas as well as database searches for *Bb s.l.* seropositive subjects.

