5.3 Inferential analysis

- In general, all statistical tests comparing treatment groups in the immunogenicity analysis will only include the two dose groups chosen for the main phase (i.e. VLA15 135 μ g and 180 μ g groups) and the placebo group. However, summary measures for 90 μ g group will be included in the tables.
- ANOVAs with factors treatment group and study sites will be performed for the comparison between the VLA15 135 μ g, 180 μ g and Placebo group for each OspA ST1 to ST6 respectively. The primary immunogenicity analysis will be the ANOVA for ELISA GMTs at Day 85 in the PP Population.
- ANOVAs will be performed for GMTs as well as GMFRs at all available time points.
- This will be done using log10 transformed data and taking the anti-log of the resulting point estimates for the least squares means, least squares means differences and the corresponding 95% CIs. Tukey's HSD test will be applied for pair-wise comparisons.
- Sensitivity analyses for GMTs and GMFRs will be performed for ANOVAs with factors study site, treatment group, study site*treatment group, age, and B.b. s.I serostatus at baseline.
- Summary tables for the OspA- specific IgG titer against each OspA serotype and summary tables for the geometric mean fold-rise against each OspA serotype will be amended by an overall test (Kruskal-Wallis).
- SCRs will be compared using Fisher-Freeman-Halton tests, a significant overall test will be amended by pair-wise tests (Fisher's exact test). The same will be done for rates of subjects reaching a 4- or 10- fold Increase from Day 1 (Visit 1) in titer.
- A non-parametric correlation analysis (Spearman) between OspA IgG antibodies GMTs for each combination of two different OspA specific IgG types will be performed for Day 85 and VLA15 treatment group separately as well as for all VLA15 treatment groups together (pooled analysis).

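### The primary Day 85 ANOVA pools two randomisations with different allocation ratios and has no phase term, so the vaccine-placebo contrasts can carry a small bias; the 135 vs 180 µg contrast cannot.

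*SAP*

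**What the plan says.** Section 1.2 describes two randomisations. In the Run-in, "a total of 120 subjects aged 18 to 40 years were to be randomized stratified by study site 1:1:1:1" to 90 µg, 135 µg, 180 µg or placebo ("30 subjects per treatment group"). In the Main Study, "a total of 450 subjects aged 18 to 65 years will be randomized stratified by study site, age group and baseline" *B.b. s.l.* serostatus, giving 180, 180 and 90 subjects on 135 µg, 180 µg and placebo. Section 2.4 confirms the ratio: "serostatus 2:2:1 in the Main Study Phase according to a randomization list created by a statistician".

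Section 2.1 says that "data from respective dose groups from the Run-in phase will be pooled for this and all further analyses", and Section 2.12 repeats the pooling rule. For the primary comparison of 135 µg, 180 µg and placebo, Section 5.3 says that "ANOVAs with factors treatment group and study sites will be performed". The sensitivity ANOVA adds the site-by-treatment interaction, age and baseline serostatus; the titles of Tables 14.1.3.1.36-41 and 48-53 show that age enters as age group. Neither model contains study phase. No immunogenicity table in Section 7.1.3 is split by phase or restricted to Main Study subjects.

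**The concern.** Phase determined the allocation ratio. Among the three compared arms, placebo is one third of the Run-in and one fifth of the Main Study. After pooling, phase is therefore associated with vaccine versus placebo by design, and randomisation within each phase does not remove that association. Any difference in titre between the phases, for example from the narrower Run-in age range, can then leak into the dose-placebo contrasts and add to the residual variance.

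The terms already planned do not reliably cover this. Site does so only if no site took part in both phases, and the SAP does not say whether that is so. Age group, in the sensitivity model, does so only in part: every Run-in subject (18-40) falls in the 18-49 group and so cannot be separated from the Main Study subjects in that group.

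At stake are the accuracy of the vaccine-placebo ratios, a little precision, and the ability to see whether the primary result holds in the Main Study alone.

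**Working it through.** **The plan's own figure.** Section 1.4 gives GMTs of 61.3 and 86.1, log10 SD 0.51, two-sided 5% and 189 per-protocol subjects per group (90% of 210).
- log10(86.1/61.3) = log10(1.405) = 0.1475.
- Unadjusted t-test power at 189 per group is 80.1% (80.3% by the normal approximation). The stated 80% is reproduced.

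**Run-in share after pooling** (sizes from Section 1.2).
- Each dose group: 30/(30 + 180) = 14.3%.
- Placebo: 30/(30 + 90) = 25.0%.
- Difference: 10.7 percentage points.

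**Assumed phase shift.** The document gives none. A shift s of 0.1 to 0.3 log10, equal in all arms, is assumed throughout.

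**Vaccine-placebo bias without a phase term.** Bias = (0.250 − 0.143) × s.
- s = 0.1: 0.0107 log10, a factor of 1.025.
- s = 0.3: 0.0321 log10, a factor of 1.077.
- Standard error = 0.51 × √(1/189 + 1/108) = 0.0615, where 108 assumes the same 10% exclusion in placebo (90% of 120). The bias is 0.17 to 0.52 standard errors.

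**Does the site factor help?** A least-squares check used ten sites and a 1.5-fold phase effect (0.1761 log10).
- Every site in both phases, with equal shares: bias 0.0189 log10, which is the full 0.107 × 0.1761.
- No site in both phases: bias zero.

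**135 vs 180 µg.** Both phases allocate these arms equally (30:30 and 180:180), so the bias is zero for any s. The cost is added within-arm variance, p(1 − p)s² with p = 0.143, against 0.51² = 0.2601.
- s = 0.1: 0.0012, or 0.5%; power 79.9%.
- s = 0.3: 0.0110, or 4.2%; power 78.5%.
- Largest loss: 80.1 − 78.5 = 1.6 points.

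**With a phase term.** The bias from an additive phase effect is zero. The 135 µg minus placebo standard error goes from 0.0615 to 0.0619 (about 0.6% larger). The 135 minus 180 µg standard error stays at 0.0525.

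**Main Study only.** With 162 per dose group (90% of 180), power for 61.3 vs 86.1 is 74.0%, against 80.3% pooled (both by the normal approximation).

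**Weighting of least-squares means.** With a phase factor, default SAS least-squares means give each phase 50% weight.
- Model GMTs would then lie 10^(0.5s) from the Main Study value: 12% at s = 0.1 and 41% at s = 0.3.
- Observed-margin weights over the three compared arms give Run-in 90/540 = 16.7%. The distance is then 10^(0.167s), or 4 to 12%.
- Without a phase term, the pooled dose-group GMTs lie 10^(0.143s) away, or 3 to 10%.

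**The case against.** Pooling is the stated design: Section 1.4 sizes the trial on 210 per dose group and 120 placebo. The primary objective is the optimal dose, and the contrast that serves it is unbiased. A pooled GMT is a different weighting of the two phases from a Main Study GMT and is not in itself an error. All of this stands.

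The placebo bias needs two conditions, and neither is documented. First, some sites must have taken part in both phases. Second, placebo titres must shift along with vaccine titres. Section 5.2 replaces negative results and results below 40 U/mL by 20 U/mL. If placebo titres sit there and phase acts only in vaccinees, the contrast is not confounded; it is a mix of the two phases' vaccine effects. Section 1.4 also gives placebo a limited role, internal validation. These limits stand too, and they keep the point small.

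Nor is phase unrecorded. Listing 16.2.1.1.1 carries the study part for each subject and Listing 16.1.3.1 the titres. What is missing is any summary or model that uses phase.

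A reader might infer that Run-in sera were measured with a different assay version. Section 2.1 mentions an earlier analysis that "covered descriptive immunogenicity analysis of selected time points of subjects from the run-in phase only", and Section 2.14 says "Due to optimization of the ELISA assay, the definition for seroconversion for ELISA results was adjusted as compared to the protocol". The documents do not support that inference. Section 2.14 reports only a changed definition of seroconversion, Section 5.2 applies one quantitation limit to all ELISA samples, and nothing says that the phases were assayed differently.

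**Conclusion.** The point holds as a minor one. The pooled primary model omits a factor that set the allocation ratio, and the vaccine-placebo contrasts can be biased as a result. For an assumed 0.1 to 0.3 log10 phase shift common to all arms, with sites shared evenly across phases, the bias is 0.011 to 0.032 log10 (2.5 to 7.7%), at most about half a standard error. It is smaller with partial site overlap, and zero if no site overlapped or if placebo titres do not shift.

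A reader might infer that the choice between 135 and 180 µg is compromised. It is not: equal allocation of these arms in both phases removes any bias from an additive phase effect, and the loss is at most about 1.6 points of power.

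The figures take Section 5.3's restriction of tests to 135 µg, 180 µg and placebo as it stands. Section 2.14 says instead that all dose groups are included in the comparison. The two should be reconciled, because the 90 µg group is entirely Run-in and these figures would not apply to it.

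**What to change.** - In Section 5.3, add study phase (Run-in/Main), or site-by-phase strata, as a fixed factor in the Day 85 GMT and GMFR ANOVAs.
- State that least-squares means use observed-margin weights, so that the Run-in does not receive half the weight. A phase factor without this statement would protect the contrasts but move the reported model GMTs further from the Main Study value than they are now.
- Repeat the Day 85 primary ANOVA (Tables 14.1.3.1.30-35) in Main Study subjects only, labelled as a supportive sensitivity analysis.

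The cost is SAP wording, one degree of freedom per model (more with site-by-phase strata), a vaccine-placebo standard error about 0.6% larger, and six extra tables. Those tables will have wider confidence intervals, with about 74% power at 162 per dose group, so they should support the pooled result and not replace it. No new data are needed, since study part is already recorded.
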